#### **9.1.1 Immune Cell Subsets:**

- Effector memory cells ( CD 45RA-CCR7-/CD62-) 
- Th17 cells 
- Tregs ( CD4+CD25+CD127-) 
- TRECS (T cell receptor excision circles) 
- CD3+ Cells ( T con) 
- CD 19+( B cell marker ) 
- CD3-CD16+CD56+( NK cells) 
- FoxP3 gene methylation status

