### 2.1.2 Extracorporeal photopheresis (ECP)

Extracorporeal photopheresis (ECP) has emerged as a promising modality to treat steroid refractory cGVHD. The procedure entails ex vivo treatment of leukapheresed patient lymphocytes with a photoactivatable compound and irradiation by ultraviolet A (UVA), followed by reinfusion of treated white blood cells (WBCs) back into the patient. ECP was initially applied in the treatment of cutaneous T-cell lymphoma (CTCL) and subsequently also in the treatment of acute and chronic graft-versus-host disease (GVHD), autoimmune disorders, and heart and lung transplant rejection. The clinical efficacy of ECP has been attributed to an immune modulatory effect and selective immune tolerance in some cases. The exact mechanism remains unknown; however, the following mechanisms of action are proposed;

- Clearance of apoptotic cells by antigen-presenting cells results in differentiation of those cells into a more tolerogenic phenotype leading to decreased stimulation of effector T cells or their deletion.
- Production of anti-inflammatory cytokines, especially interleukin 10, is increased
- Production of pro-inflammatory cytokines, especially interleukin 12 and TNF $\alpha$ , is decreased.
- Generation of CD4+, CD25+, GITR+, Foxp3+, CD62L+ T-regulatory cells.
- Generation of monocyte-derived, tolerogenic dendritic cells has been postulated to contribute to the downregulation of immune response in GVHD.

One study evaluated the percentage of functional T-regs after 6 ECP procedures demonstrating an increase from 8.9 to 29% of the total circulating CD4+ cells. ECP is an apheresis-based therapy, where approximately  $5 \times 10^9$  transplant-recipient leukocytes are treated with a photoactivatable 8-methoxysoralen (8-MOP), followed by exposure to approximately 1.5 Joules/cm^2 of UVA light and reinfusion of treated leukocytes to recipients in a closed-loop system.

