Koreth and colleagues conducted a phase I trial of low-dose IL-2 for patients with steroid-refractory chronic GVHD. A total of 29 patients were enrolled. The highest dose level induced unacceptable constitutional symptoms. The maximum tolerated dose of interleukin-2 was  $1 \times 10^6$  IU per square meter. Of the 23 patients who could be evaluated for response, 12 had major responses involving multiple sites. None had progression of chronic GVHD or relapse of a hematologic cancer. The numbers of CD4+ T-reg cells were preferentially increased in all patients, with a peak median value, at 4 weeks, that was more than eight times the baseline value ( $P < 0.001$ ), without affecting CD4+ conventional T cells (T-con). The T-reg:T-con ratio increased to a median of more than five times the baseline value ( $P < 0.001$ ). The T-reg cell count and T-reg:T-con ratio remained elevated at 8 weeks ( $P < 0.001$  for both comparisons with baseline values), then declined when the patients were no longer receiving interleukin-2. The increased numbers of T-reg cells expressed the transcription factor forkhead box P3 (FOXP3) and were able to inhibit autologous T-con cells. Immunologic and clinical responses were sustained in patients who received IL-2 for an extended period, permitting the glucocorticoid dose to be tapered by a mean of 60% (range, 25- 100). Additionally we have in house experience with use of single agent IL-2 (n=7) in patients who have been treated with ECP in the past. In these patients with steroid refractory cGVHD, all patients have derived clinical benefit, either partial response or stable disease, with no serious Grade III/IV adverse events noted at the dose level of 1 million Units /m^2

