Dander et al. studied the role of IL-17-producing CD4+ T cells (TH17) in cGVHD in the serum of 51 patients post allo-HCT with clinical manifestations of cGVHD, and compared this to 15 healthy donors (HD). Patients with cGVHD showed an increase of TH17 population compared with HD (mean SFU=178/25000 cells, n=18, ANOVA  $P < 0.001$ ). Importantly, by analyzing the proportion of TH17 cells according to the activation status of cGVHD (active vs. inactive phases), the authors were able to demonstrate that patients with active cGVHD, show an increase in the TH17 population (mean spot forming units [SFU] =237/25000 cells, n=13, ANOVA  $P < 0.001$ ). Inflammatory cytokines produced by TH17 cells - IL-6, TNF- $\alpha$  and IL-8 - were also significantly elevated in patients with active cGVHD. Hence the TH17 T cell subset by virtue of its secreted cytokines may be a useful adjunct to cGVHD assessment. In this analysis, CD 4+ T cells were selected by immunomagnetic beads using the Miltenyi system, plated in graded numbers and stimulated by 12-phorbol 13-myristic acid (50 ng/mL) and ionomycin (2g/mL) for 16 hr to elicit IFN- $\gamma$  production.

T-reg cells constitute 5-10% of circulating CD4+ T cells and suppress auto- and allo-reactive T cell clones. Loss of T-reg cells has also been associated with clinical symptoms of cGVHD. Phenotypically, T-reg cells are CD4+ and CD25+ and express forkhead transcription factor FOXP3. Zorn et al. evaluated CD4+CD25+ T-reg cells in 30 patients with cGVHD after allogeneic HSCT, 27 patients without active cGVHD, and 26 healthy controls. They also evaluated TREC (T cell receptor excision circles) by peripheral blood PCR as a marker of thymic activity in post HCT patients. Patients with active cGVHD had significantly lower expression of FOXP3 when compared with patients without cGVHD ( $P = 0.009$ ) or healthy donors ( $P = 0.01$ ). Patients with cGVHD showed a significant decrease in TREC compared with healthy donors ( $P < 0.001$ ); supporting that thymic function is substantially impaired following allogeneic HCT.

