Natural Killer cells (NK cells), B cells and T cell subsets were studied as part of immune reconstitution post allo-HCT prospectively by Abrahamsen et al. in 57 patients. Blood and bone marrow samples were collected 3, 6, and 12 months after transplantation for analysis of immune reconstitution. Flow cytometric analysis was used for phenotyping T cell subsets. To assess the effect of chronic GVHD on immune reconstitution, patients with extensive cGVHD were compared to patients with no or limited chronic GVHD. The authors noted that extensive cGVHD is associated with elevated CD3+ T cells with relative decline in CD19+ B cells and CD3+CD16+/56+ NK-cells.

Inflammatory biomarkers have also been used to follow patients with cGVHD. Dander et al. studied peripheral blood samples obtained from 51 patients post allogeneic cell transplantation and patients developing GVHD were monitored for presence of TH-17 cells by ELISPOT or flow cytometry. The TH-17 cell population was increased (up to 4.8% of peripheral blood CD4+T lymphocytes) in patients with acute GVHD and (up to 2.4%) in patients with active chronic GVHD along with an inflammatory process. TNF- $\alpha$  was significantly increased in patients presenting with aGVHD (mean 49 pg/mL, range 3.6–176 pg/mL, n=10) and cGVHD (mean 28 pg/mL, range 4.8–77 pg/mL, n=14). Similarly, IL-6 levels were strongly enhanced in patients with aGVHD (mean 62 pg/mL, range 1–407 pg/mL) and active cGVHD. IL-8 cytokine levels were significantly elevated in patients with aGVHD (mean 20.8 pg/mL, range 3.9–49.1 pg/mL) and active cGVHD (mean 22.4 pg/mL, range 3.8–125 pg/mL) compared with healthy donors.

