### **9.1 Immune Correlative Studies:**

Chronic GVHD is associated with a deficiency of T-reg, NK cells and naive CD8+ T cells. Studies support increased pro-inflammatory cytokines in chronic GVHD cases, including TNF- $\alpha$ , IL-6, IL-1 $\beta$ , IL-8, soluble alpha chain of the IL-2 receptor shed by activated T cells (sIL-2R) and IL-1R $\alpha$ , among others and decrease in anti-inflammatory cytokines such as IL-10. Early-onset chronic GVHD had increased soluble B cell activating factor (sBAFF), anti-dsDNA, sIL-2R $\alpha$  and sCD13. Late-onset chronic GVHD cases had increased sBAFF and anti-dsDNA. Additionally, early onset chronic GVHD demonstrates decreased IFN- $\gamma$  and IL-2, while late-onset chronic GVHD had decreased IL-4, IL-2 and FOXP3. CRP and C3 and C4 complement levels are also elevated in cGVHD.

The primary immunologic endpoint is a fold-increase in T-reg and the T-reg/-Tcon ratio at 3 months of (ECP+IL2) therapy. Protocol-specified immunophenotypic analyses will be performed at baseline and at 3, 7, 9 & 12 weeks during treatment with ECP +IL-2 and 4 weeks after discontinuation of combination therapy (week 16 for those who complete treatment).

The following analysis will be performed:

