3) Study miRNA expression in Tcon with or without Treg suppression: Experimental approach: Peripheral blood mononuclear cell (PBMC's) from all enrolled patients will be extracted from whole blood using Ficoll paque density gradient centrifugation (GE healthcare) at baseline. The PBMC's will then be flow sorted into 95% pure population of Tregs (CD4+CD25+CD127-) and Tcons (CD4+CD25+CD127-) using FACSaria cell sorter (BD Biosciences). Co-culture of Tregs and Tcons will be done in 96 well round bottom plates (Corning star, Cambridge, MA). Cells will be plated at

density of  $1 \times 10^5$ /cells/well in RPMI 1640 media (0.2mL/well) and incubated at 37C for 72 hours. Cultures will be stimulated by 1 $\mu$ gm/mL anti-CD3 antibody (BD PharMingen, San Diego, CA). miRNA expression of Treg suppressed and Treg unsuppressed Tcons will be investigated by miRCURY LNA™ microRNA Array (Exiqon, Vedbaek, Denmark). The intensity of signal will be calculated after background subtraction. The threshold value to screen up or down regulation of miRNAs will be a fold change  $\geq 2.0$  or  $\leq 0.5$ . Analysis Plan: The specific time trend for each cell subset, cytokine and miR will be assessed using linear mixed effects modeling. The overall fit of the model will be evaluated graphically by taking a scatter plot of data for each and applying an overlay of the line generated by the model. An evaluation of the regulation patterns over time will be assessed by examining the slope patterns. To assess the possible impact of changes in expression on T cells, functional regression modeling will be used. Similar modeling techniques will be used to assess the impact of clinical events on expression.

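### Tcon, the denominator of the primary immunologic ratio, is labelled as all CD3+ cells, while the historical ratio quoted in the protocol uses CD4+ conventional T cells; the sort in 9.2.2 also gives Treg and Tcon one phenotype

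*Combined protocol and SAP*

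**What the plan says.** Section 9.1 sets the endpoint: "The primary immunologic endpoint is a fold-increase in T-reg and the T-reg/-Tcon ratio at 3 months of (ECP+IL2) therapy". No section writes the ratio out as a formula.

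Tcon is given a phenotype in three places:

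- Sections 5.8.1 and 9.1.1 carry the same list entry, "CD3+ Cells ( T con"). In those lists Treg is CD4+CD25+CD127-.
- Section 9.2.2, item 3, describes a baseline cell sort into "Tregs (CD4+CD25+CD127-) and Tcons (CD4+CD25+CD127"-). The two phenotypes are identical.

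The historical benchmark is the phase I trial of low-dose IL-2 summarised in section 2.1.3. It reports that Tregs rose "without affecting CD4+ conventional T cells (T-con"), and then: "The T-reg:T-con ratio increased to a median of more than five times the baseline value".

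The flow panel in section 9.2.1 includes CD3, CD4, CD25 and CD127.

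**The concern.** A ratio endpoint needs one stated denominator. Read literally, the list entry makes that denominator every CD3+ cell. This differs from the phase I denominator in two ways: it adds the CD8+ and other non-CD4 T cells, and it counts the Tregs in both numerator and denominator. The second feature compresses any fold-increase, because the denominator grows as the Tregs grow. The source cited for the entry does not help. Section 2.1.5 describes that study as reporting that "extensive cGVHD is associated with elevated CD3+ T cells", and does not present CD3+ cells as conventional T cells.

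At stake is whether the trial's ratio result is on the same scale as the one ratio figure in the protocol that a reader would naturally set it against. If the denominator stays open, it could also be chosen after the data are seen.

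The sort is a separate matter. With one phenotype for both populations, the procedure as written cannot produce separate Treg and Tcon fractions for the co-culture.

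**Working it through.** The plan gives no target, threshold or precision for the ratio, so there is no design figure to reproduce. The check is how one and the same biological change reads under each denominator.

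**Inputs**

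- r, Treg as a share of CD4+ cells: 0.05 to 0.10. Section 2.1.5 says "T-reg cells constitute 5-10% of circulating CD4+ T cells".
- CD4-based ratio rise: 5-fold, the lower bound of the phase I figure in section 2.1.3.
- ECP figures, section 2.1.2: "demonstrating an increase from 8.9 to 29% of the total circulating CD4+ cells".
- f, CD4+ cells as a share of CD3+ cells: not in the documents; assumed 0.3 to 0.6.
- All cells other than Tregs are assumed unchanged.

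**Formula.** Set baseline CD3+ cells to 1. CD4+ cells are then f and Tregs are rf. Let the Treg count rise F-fold.

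- Over CD4+ non-Treg cells, the denominator f(1 - r) does not move, so the ratio rises F-fold.
- Over CD3+ cells, the denominator becomes 1 + (F - 1)rf, so the ratio rises by F / [1 + (F - 1)rf].

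**A 5-fold CD4-based rise, read over CD3+**

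| r | f | Calculation | Fold over CD3+ |
|---|---|---|---|
| 0.05 | 0.3 | 5 / (1 + 4 × 0.015) | 4.72 |
| 0.05 | 0.6 | 5 / (1 + 4 × 0.030) | 4.46 |
| 0.10 | 0.3 | 5 / (1 + 4 × 0.030) | 4.46 |
| 0.10 | 0.6 | 5 / (1 + 4 × 0.060) | 4.03 |

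The reading is about 6% to 19% lower (1 - 4.72/5 and 1 - 4.03/5).

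**The ECP figures**

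- Over CD4+ non-Treg cells: (29/71) / (8.9/91.1) = 0.408 / 0.0977 = 4.18.
- Over CD3+, with F = 4.18 and r = 0.089: at f = 0.3, 4.18 / (1 + 3.18 × 0.0267) = 3.85; at f = 0.6, 4.18 / (1 + 3.18 × 0.0534) = 3.57.
- This is about 8% to 15% lower (1 - 3.85/4.18 and 1 - 3.57/4.18).
- Under a different assumption, that the CD4+ share of CD3+ cells stays constant, the fold over CD3+ is 29/8.9 = 3.26 whatever that share is.

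**The sort.** Treg and Tcon have the same three markers with the same signs, so no cell can be assigned to one and not the other. Item 3 of 9.2.2 is a baseline experiment on miRNA expression, and nothing in it enters the ratio of section 9.1.

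**The case against.** The strongest reply is that the CD3+ entry is one line in a list of assays, and that no section says it is the denominator of the ratio. The panel in 9.2.1 contains CD4, CD25 and CD127, so the laboratory can compute a CD4-based Tcon and may intend to. The first component of the endpoint, the Treg fold-increase, does not use Tcon. The endpoint is correlative and has no stated test or cut-off.

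All of this is right, and it limits the point to the written definition. It does not remove it. If the entry is only a loose label, the ratio has no defined denominator, and the correction is the same.

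A reader might infer more than the documents support:

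- *That the ratio can never be compared with the phase I figure.* The data allow a CD4-based ratio; only the wording stands in the way.
- *That a planned historical comparison of the ratio fails.* The Synopsis compares response rates with historical controls, and section 2.1.4 compares the increase in Tregs. A comparison of the ratio is at most implied.
- *That the distortion should be sized on an 8-fold rise.* In section 2.1.3 the eight-fold figure is the Treg count; the ratio figure is five-fold.
- *That CD3+ cells falling as patients improve would by itself raise the ratio.* The study described in 2.1.5 compares patients with different extents of cGVHD. It says nothing of change within patients over 12 weeks.
- *That the mixed-model slopes in 9.2.2 replace the week 12 fold-increase.* Section 9.1 fixes the time point. Section 9.2.2 does not say the fold-increase is taken from a slope, and it includes a graphical check of model fit.

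**Conclusion.** The point holds as a fault of definition. As labelled, Tcon is not the population behind the only historical ratio in the protocol. Used literally, the label would make a 5-fold CD4-based rise read as about 4.0 to 4.7, and the ECP figures as about 3.6 to 3.9 instead of 4.2. These sizes rest on an assumed CD4+ share of 30-60% of CD3+ cells and on other cells staying unchanged; the first also uses the protocol's 5-10% Treg share. The distortion is moderate and would not hide a large rise, but the result would not be on the phase I scale.

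The identical sort phenotypes are a second, independent error, probably of typing, confined to the co-culture experiment.

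The correction should be made before the ratio is analysed. It does not touch the Treg fold-increase, the clinical primary endpoint, the Simon rule or the stopping rules.

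**What to change.** 1. In 5.8.1 and 9.1.1, define Tcon as CD4+ cells outside the Treg gate, using the CD4, CD25 and CD127 markers already in the 9.2.1 panel. If total CD3+ cells are wanted as a subset, list them without the Tcon label.
2. In 9.1, write the ratio out: Treg count divided by CD4+ non-Treg count.
3. In 9.2.2, item 3, correct the Tcon phenotype so that it differs from that of Treg and agrees with the definition in step 1.

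The cost is wording in the laboratory sections. The samples, visits and antibodies stay as planned.

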#### **9.1.2 Inflammatory Markers:**

- IFN- $\gamma$ , TNF  $\alpha$  
- IL-2,IL-4,IL-6,IL-8 
- IFN- $\gamma$ , TNF  $\alpha$  
- BAFF 
- IL-2 receptor  $\alpha$  (IL2R $\alpha$ ) and hepatocyte growth factor (HGF) for systemic GVHD 
- Elafin for skin GVHD 

- Regenerating islet-derived 3 $\alpha$  (REG3 $\alpha$ ) for gastrointestinal GVHD
- Suppression of tumorigenicity 2 (ST2) for steroid-refractoriness
- CXCL9
- Micro RNA analysis

## 9.2 Methods

### 9.2.1 Immunologic Assays

Immune cell subset analysis will be performed on peripheral blood mononuclear cells (PBMCs) using the Ficoll density gradient separation. Approximately 15 ml of whole blood will be collected from patients on each visit in EDTA (lavender top) tubes and sent to the research lab for testing. Blood will transferred under a laminar flow hood into a 50mL tube and diluted 1:1 with PBS. The diluted blood will be layered on Ficoll medium by gently pipetting. The 50mL tube will be placed in a swinging bucked centrifuge and spun at 833xg for 20 minutes at 20°C, acceleration 9 and no brake. 50,000 PBMCs will then be incubated with fluorophore-conjugated monoclonal antibodies: Immunophenotyping will be done for the following markers surface markers (CD 4, CD16, CD 25, CD127, CD45RA, CD62, CD3, CD19 and CD56 to distinguish T cell subsets at baseline and with therapy. Cell analysis will be performed with the use of the FACS Canto II system (BD Biosciences) and FACS Diva software (BD Biosciences).

### 9.2.2 MicroRNA analysis:

1) Evaluate changes in miR signature in patients with steroid refractory cGVHD on combination therapy with IL-2 and ECP. Experimental Approach: Plasma samples (1 mL) will be collected at baseline (at enrollment) and at 12 weeks (completion of treatment) - from all patients enrolled on protocol. Samples will be stored at -70C freezer. Total RNAs will be extracted from batched samples using 400 $\mu$ L plasma by mirVana PARIS kit (Ambion) according to manufacturer's instructions. *Caenorhabditis elegans* miRNA (cel-miR-39) will be used as spiked in control. Plasma miRNAs will be quantified using SYBR green-based quantitative reverse-transcriptase polymerase chain reaction (qRT-PCR). To compare the plasma miR profiles of the two groups of patients, we will use qPCR-based high throughput miRNA array that contains primers specific for 345 well-characterized human miRNAs. Cel-miR-39 will be used for normalization to obtain relative miRNA expression. Statistical Analysis: Hierarchical clustering analysis will be performed using Cluster 3.0. The Mann-Whitney test will be used to compare differences in plasma miR expression between responders and non-responders. Receiver operative characteristic (ROC) curves and area under the ROC curve will be used to assess the sensitivity and specificity of miR biomarkers and logistic regression analysis will be used to develop a miRNA panel predictive of response to therapy. Based on the literature we will focus our analysis on up regulation of miR-146a and down regulation of miR-106b and miR-21.

2) Evaluate miR signature in patients with cGVHD versus matched post HCT controls without cGVHD. Experimental approach. 1 ml plasma sample will be extracted upon enrollment from (n=20) patients with severe steroid refractory cGVHD and a control group of patients without manifestations of cGVHD (n=20) who have similar HCT characteristics (obtained through the Protocol #09050. PI: [name]). Plasma samples will be batched and tested for differential miR expression as described in section above- to analyze differential miR expression pattern.

3) Study miRNA expression in Tcon with or without Treg suppression: Experimental approach: Peripheral blood mononuclear cell (PBMC's) from all enrolled patients will be extracted from whole blood using Ficoll paque density gradient centrifugation (GE healthcare) at baseline. The PBMC's will then be flow sorted into 95% pure population of Tregs (CD4+CD25+CD127-) and Tcons (CD4+CD25+CD127-) using FACSaria cell sorter (BD Biosciences). Co-culture of Tregs and Tcons will be done in 96 well round bottom plates (Corning star, Cambridge, MA). Cells will be plated at

density of  $1 \times 10^5$ /cells/well in RPMI 1640 media (0.2mL/well) and incubated at 37C for 72 hours. Cultures will be stimulated by 1 $\mu$ gm/mL anti-CD3 antibody (BD PharMingen, San Diego, CA). miRNA expression of Treg suppressed and Treg unsuppressed Tcons will be investigated by miRCURY LNA™ microRNA Array (Exiqon, Vedbaek, Denmark). The intensity of signal will be calculated after background subtraction. The threshold value to screen up or down regulation of miRNAs will be a fold change  $\geq 2.0$  or  $\leq 0.5$ . Analysis Plan: The specific time trend for each cell subset, cytokine and miR will be assessed using linear mixed effects modeling. The overall fit of the model will be evaluated graphically by taking a scatter plot of data for each and applying an overlay of the line generated by the model. An evaluation of the regulation patterns over time will be assessed by examining the slope patterns. To assess the possible impact of changes in expression on T cells, functional regression modeling will be used. Similar modeling techniques will be used to assess the impact of clinical events on expression.

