### 13.1 Study Design, Sample Size, and Accrual Rate

This single center/single arm, phase II clinical trial is designed to evaluate the anti-cGVHD activity of extracorporeal photopheresis (ECP) when combined with low dose IL-2, in patients with steroid refractory cGVHD, as assessed by overall cGVHD response rate (CR+PR+SD). The primary endpoint overall response (CR+PR+SD) is based on the NIH cGVHD consensus criteria; calculated as the percent of evaluable patients that have confirmed CR/PR or SD

This study will implement a Simon, optimal, two-stage design to evaluate the anti-cGVHD activity of the ECP/IL-2 regimen. The trial is expected to enroll 24 patients e sample size is based on the desire to discriminate a promising response rate of 50% from a current response rate of 25%. The null hypothesis

that the true response rate is 25% will be tested against a one-sided alternative. In the first stage, 9 patients will be accrued. If there are 2 or fewer responses in these 9 patients, the study will be stopped. Otherwise, 15 additional patients will be accrued for a total of 24. The null hypothesis will be rejected if 10 or more responses are observed in 24 patients. This design yields a type I error rate of 0.05 and power of .80 when the true response rate is 50%. Currently, about 20-25 new patients are referred to ECP per year. We expect that 6 patients to be enrolled per year with the expected completion of accrual in 4 years.

**Evaluable for Response:** As part of the primary analysis, patients will be considered evaluable for response if they are eligible, have baseline disease assessments, and receive protocol treatment of any duration. All such patients will be evaluated for clinical response. Our primary outcome will be the clinical response rate measured in all patients who are enrolled and receive any amount of protocol therapy.

Patients who are consented for the study but withdraw for any reason (progression of GVHD, infectious complications, insurance denial etc) prior to initiation of protocol therapy will not be eligible for response evaluation.

**Evaluable for Toxicity:** Patients will be considered evaluable for toxicity if they receive any study drug.

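### The miRNA response panel has no stated selection rule, multiplicity control or internal validation; if it is selected from the 345-miRNA array, its in-sample AUC would be badly inflated

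*Combined protocol and SAP*

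**What the plan says.** Section 9.2.2, item 1, takes plasma at baseline and week 12 from all enrolled patients and profiles it on an array with "primers specific for 345 well-characterized human miRNAs". Hierarchical clustering comes first. Mann-Whitney tests then compare responders with non-responders, ROC curves and AUC give the sensitivity and specificity of the markers, and "logistic regression analysis will be used to develop a miRNA panel predictive of response to therapy". The next sentence says that the analysis will focus on three miRNAs chosen from the literature, each with a direction: miR-146a up, miR-106b and miR-21 down.

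Item 2 of the same section compares 20 patients with cGVHD with 20 transplant controls without it. The analysis plan at the end of item 3 covers time trends by mixed models and functional regression. Section 13.2 does not mention miRNA.

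On sample size, Section 13.1 says "The trial is expected to enroll 24 patients" and also "If there are 2 or fewer responses in these 9 patients, the study will be stopped".

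None of these sections gives an adjustment for multiple testing, a panel size, a selection rule, cross-validation, a bootstrap or a hold-out set.

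**The concern.** A predictive panel needs a measure of how well it would predict in patients who were not used to build it. Here there are up to 345 candidates and at most 24 patients, and no other data set carries the outcome. The controls in item 2 have no cGVHD and so no response, which means that they cannot test a response panel.

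With so many candidates per patient, the best few markers separate the two groups well by chance, and a logistic model fitted to them separates them better still. An AUC from the same patients then measures the search and not the biology. A reader who sees a sensitivity, a specificity and an AUC for a predictive panel may take them as performance. An exploratory label does not correct the number.

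**Working it through.** **1. Sample size (Section 13.1).** The miRNA analysis has no sample size of its own, so it inherits that of the Simon design: stop at 2 or fewer responses in 9, and "The null hypothesis will be rejected if 10 or more responses are observed in 24 patients".

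P(reject | p) = Σ over x = 3 to 9 of P(X₁ = x) · P(X₂ ≥ 10 − x), with X₁ ~ Bin(9, p) and X₂ ~ Bin(15, p).

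- p = 0.25: 0.0485, against a stated 0.05.
- p = 0.50: 0.805, against a stated 0.80.
- Probability of stopping at 9: 0.60 at p = 0.25 and 0.09 at p = 0.50.

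The stated design is reproduced. The panel has at most 24 patients, possibly 9, and fewer where a week-12 sample is missing. (Section 3.3 speaks of 17 to 37 subjects; I use Section 13.1.)

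**2. One-at-a-time screen, no true association.** At a two-sided 0.05, the expected number of false positives among 345 is 345 × 0.05 = 17.25. If the markers are independent, the chance of at least one is 1 − 0.95³⁴⁵ > 0.9999. For the three named miRNAs it is 1 − 0.95³ = 0.143.

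**3. Panel, no true association.** For each simulated data set I drew 345 noise markers and ranked them by AUC = (R₁ − n₁(n₁+1)/2)/(n₁n₀), where R₁ is the responders' rank sum. The best k went into a logistic model (tiny ridge for stability), and the AUC was taken on the same patients. There were 1,000 runs for the 12/12 top-3 case and 500 for the others. The documents give no k, selection rule, split or correlation; all are assumptions, as is a single time point. Correlation was varied at 12/12 only, in 15 blocks.

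| Responders/non-responders | Correlation | Panel | Mean AUC (5th–95th percentile) | Share ≥ 0.90 |
|---|---|---|---|---|
| 12/12 | 0 | best single | 0.86 (0.81–0.92) | – |
| 12/12 | 0 | top 3 | 0.957 (0.90–1.00) | 0.94 |
| 12/12 | 0 | top 5 | 0.991 (0.95–1.00) | 0.998 |
| 12/12 | 0.5 | top 3 | 0.930 (0.86–1.00) | 0.78 |
| 12/12 | 0.8 | top 3 | 0.880 (0.79–0.965) | 0.36 |
| 16/8 | 0 | top 3 | 0.968 (0.91–1.00) | 0.97 |
| 18/6 | 0 | top 3 | 0.981 (0.935–1.00) | 0.99 |
| 20/4 | 0 | top 3 | 0.995 (0.96–1.00) | 1.00 |
| 12/12 | 0 | three fixed in advance | 0.689 (0.56–0.83) | 0.007 |
| 20/4 | 0 | three fixed in advance | 0.757 (0.59–0.94) | 0.11 |

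The true AUC is 0.50 in every row. Unequal splits are plausible. Section 13.1 counts stable disease as response, and Section 2.1.3 reports partial response or stable disease in all seven in-house patients. Section 13.2 defines response as CR+PR, so the responder label for this analysis is itself not settled.

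**4. If the trial stops at 9.** The futility rule then leaves at most 2 responders. At 2/7, one noise marker separates the groups perfectly with probability 2/C(9,2) = 2/36 = 0.056. Among 345 that is about 345 × 2/36 = 19 perfect markers, so an in-sample AUC of 1.00 is practically certain if the markers are independent. A simulated 5/4 split, which the futility rule itself cannot produce, gave 1.00 in every run.

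**5. Effect of a remedy.** With selection repeated inside stratified 4-fold cross-validation (12/12), the mean null AUC was 0.505 for the top-3 panel (5th–95th percentile 0.28–0.78) and 0.502 for the top-5 panel. Three fixed markers gave 0.49. Pooled leave-one-out with a three-marker Firth model gave a null mean of about 0.38 to 0.40, which is biased downward.

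**6. Bonferroni.** The threshold for the array is 0.05/345 = 0.000145. At 20/4 the smallest exact two-sided Mann-Whitney p is 2/C(24,4) = 2/10,626 = 0.000188, so the threshold could never be met.

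**The case against.** The strongest reply is that the plan never says the panel is picked as the best few of 345. It gives no selection rule at all, and the sentence after the one on the panel names three miRNAs with directions. On that reading the null in-sample AUC is about 0.69 at 12/12 and reaches 0.90 in fewer than 1 run in 100. A reader might infer from Section 9.2.2 that the reported AUC is bound to look excellent. The documents do not support that: it follows only if the panel is selected from the array.

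A reader might also infer that the sponsor has chosen to test every one of the 345 markers singly and to report an uncorrected AUC. The text does not say so; it is silent on both. Nor does any single figure such as 0.96 follow from the plan, since panel size, split and independence are assumptions, and strong correlation lowers the result to 0.88.

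These limits stand. They do not remove the point. A focus is not a restriction, and nothing ties the panel to the three miRNAs. Even a three-marker panel would show about 0.69 in-sample where the truth is 0.50.

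**Conclusion.** The point holds as a gap in specification with a conditional consequence. If the panel is selected from the array, noise alone would give a mean in-sample AUC of about 0.88 to just over 0.99 at 24 patients, under the assumptions in the table. If it is confined to the three named miRNAs, the range is about 0.69 to 0.76.

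It is a minor point for the trial as a whole. The panel is not among the objectives in Section 1, the endpoints in Section 11 or the analyses in Section 13.2, and no stopping rule or treatment decision uses it. A reader might infer that the trial's main conclusion is at risk; it is not, because the primary endpoint and the Simon design do not depend on this analysis.

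**What to change.** Amend the statistical paragraph of Section 9.2.2, item 1, before the batched samples are analysed:

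- Either limit the response panel to miR-146a, miR-106b and miR-21, or state the selection rule and panel size and repeat all marker selection inside each resample.
- Report the AUC from repeated stratified k-fold cross-validation, with an interval. Bootstrap optimism correction is an alternative, with a note that some optimism remains at this size. Do not use pooled leave-one-out. The interval will be wide, as step 5 of the working shows.
- Report the 345-miRNA screen with Benjamini-Hochberg false-discovery control and label it hypothesis-generating.
- State which responder definition and which time point the panel uses.

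The cost is analysis text and code, with no added patients, samples or assays. The reported AUC will be less favourable.
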